10.6.1	General Duties	32
10.6.2	Ethics Committee Communication.....	33
10.6.3	Investigator Records.....	33
10.6.4	Investigator Reports	34
10.7	Sponsor Responsibilities	34
10.7.1	General Duties	34
10.7.2	Sponsor Records	34
10.8	Registry Changes.....	34
10.9	Audits and Inspections.....	35
10.10	Publication Policy.....	35
APPENDIX A:	REFERENCES	36
APPENDIX B:	ABBREVIATIONS AND ACRONYMS.....	42

REGISTRY SYNOPSIS

Title	Edwards PASCAL Transcatheter Valve Repair System Registry: A multicenter observational registry with the Edwards PASCAL Transcatheter Valve Repair System
Phase	Post Market Observational Registry
Sponsor	Edwards Lifesciences, LLC [name] [name]
Sponsor Contact	[REDACTED]
Device Name	Edwards PASCAL Transcatheter Valve Repair System
Indications for Use	The Edwards PASCAL Valve Repair System is indicated for the percutaneous reconstruction of an insufficient mitral valve.
Background	This registry will collect prospective and retrospective clinical data on patients treated with the Edwards PASCAL Transcatheter Valve Repair System outside of the Post Market Clinical Follow-up (PMCF) study. Patients will be treated per standard of care at their medical facilities and a written informed consent will be collected to allow the data to be collected. This registry intends to enroll patients under commercial usage and will serve as a mechanism to collect clinical data to further characterize the safety, performance and effectiveness of the PASCAL Transcatheter Valve Repair System.
Registry Objectives	To expand the knowledge of safety, performance and effectiveness of the Edwards PASCAL Transcatheter Valve Repair System.
Registry Design	A post market, prospective and retrospective (where applicable), observational, single-arm, multicenter, registry. Data will be collected on patients receiving the implant in the commercial setting. Available clinical data will be collected prospectively, as it becomes available. Retrospective data collection is allowed for all patients treated in the commercial experience (where applicable). Data on patients will be collected as it becomes available.

Registry Design (cont.)	All participating patients will provide a written informed consent to allow data to be collected in compliance with local privacy laws and regulations.
Data Collection	
Patient data, as per the CRF, will be collected.
 
Clinical and echocardiographic data available from routine clinical records will be captured at the following time points:
 
 • Baseline: pre-procedural data • Procedural data: data collected as part of the procedure • Discharge data: data collected prior to discharge from hospital • 30 day visit: visit performed between discharge and up to 2 months post procedure • 1 year follow up: visit performed between 10 months and 14 months post procedure
Number of Patients	A minimum of 200 patients will be enrolled in the Registry.
Number of Medical Centers	A minimum of 10 sites in the European Union.
Outcome Measures	
Primary Safety Measures:
 
 • Major Adverse Events (MAE) at 30 days. MAEs – composite of all-cause death, Myocardial Infarction, Stroke, Heart Failure Hospitalization, or complication requiring transcatheter or surgical intervention (repeat PASCAL or Mitral Valve Surgery) 
Primary Performance Measure:
 
 • MR reduction to ≤2+ at 30 days and 12 months 
Secondary Measures:
 
 1. Adverse event assessment (all follow up visits) 2. EQ-5D-5L or KCCQ at baseline, 30 days and 12 months, if available 3. 6MWT at baseline, 30 days, and 12 months, if available 4. NYHA assessment at baseline, 30 days and 12 months, if available

Statistical Analysis	No predefined statistical hypothesis testing will be performed. Only descriptive and summary statistical analysis will be provided for baseline/pre-procedure, procedure, and other follow-up outcome variables.
Enrollment Criteria (Inclusion)	
Patients must meet ALL of the following criteria to be eligible for the registry:
 
1. Patients electively treated or electively intended to be treated with Edwards PASCAL Transcatheter Valve Repair System2. Patients provided written informed consent to participate in the registry.
Enrollment Criteria (Exclusion)	
Patients will be excluded from the Registry if they meet the following:
 
1. Patient is part of an ongoing Edwards Pre or Post Market Clinical study for the PASCAL Transcatheter Valve Repair System.

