3.3 Number of Planned Patients

All patients treated with the commercially available PASCAL Transcatheter Valve Repair System and who are not part of any ongoing PASCAL pre or post market study, will be asked to participate in this registry. A minimum of 200 patients are expedited to be enrolled in the registry at sites performing transcatheter valve repair where commercialized PASCAL Transcatheter Device is available.

A patient will be considered enrolled in the registry once the patient has signed the ICF and the procedure has begun (defined as PASCAL guide sheath is inserted into the vasculature).

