3.5 Inclusion Criteria

Patients must meet all of the following criteria to be eligible for the Registry:

1. Patients electively treated or electively intended to be treated with Edwards PASCAL Transcatheter Valve Repair System.
2. Patient provided written informed consent to participate in the registry.

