3.7 Registry Exit Criteria and Procedures

The reason for exit from the registry will be documented on the appropriate case report forms and in the medical records for each patient who exits the registry.

Patients may exit the registry for any of the following reasons:

- Completion per Protocol
- Withdrawal
 - Patient Withdrawal: The patient may voluntarily withdraw from the registry at any time, without penalty or loss of benefits to which they are otherwise entitled.
 - Physician Withdrawal: The Investigator also has the right to withdraw a patient if s/he feels it is in the best interest of the patient to do so.
 - Sponsore Withdrawal: The Sponsor may prematurely terminate the Registry.
- Death
- Device Reintervention or Explant
 - Patients who have a surgical reintervention where the device is explanted will be followed for 30 days post-reintervention or until resolution of any adverse events related to the procedure and then exited from the registry. Patients that have a percutaneous or surgical reintervention where the device remains in place will continue to be followed for the duration of the registry.

- Lost to Follow-up
 - If a patient cannot be reached for a follow-up visit, the Investigator will document the contact efforts made to the patient and/or effort to obtain hospital records in the appropriate electronic case report form. If the patient cannot be reached in any way, or misses a visit, the patient will be considered “unable to contact” for that time interval. After three (3) documented unsuccessful attempts to make contact prove unsuccessful, a certified letter will be sent to the patient’s residence. If there is no response after the certified letter is sent, the patient will be considered “lost to follow-up”.
 - For patients who are lost-to-follow-up or withdraw early, Edwards may request the site to search death registries as available or applicable per GDPR requirements and may request the site to obtain the death certificate, if applicable.

In all cases of withdrawal (as described above), no additional data will be collected.

All data collected up until the time of withdrawal will be analyzed and will be retained for the duration of the registry.

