4.3 Informed Consent

The registry investigator(s) and/or delegated registry personnel will approach patients who are candidates for treatment with the PASCAL System to assess their interest in participating in the registry by providing them an overview of the registry. If patients are interested in allowing their data to be used for the registry, the patient will sign the EC-approved informed consent form (ICF) prior to any data being collected.

A patient will be considered enrolled in the registry once the patient has signed the ICF and the procedure has begun (defined as PASCAL guide sheath is inserted into the vasculature).

The Sponsor must approve any modifications to the Informed Consent Form prior to submission to the EC, and/or local regulatory agencies (as required).

Failure to provide informed consent renders the patient ineligible for the registry.

The consent form will be written in the native language of the patient and administered only by the Investigator or EC-approved persons.

The Investigator or delegated person administering the consent must sign and date the ICF to indicate that the purpose of the registry were explained to the patient.

The signed ICF must be retained by the registry site for verification during on-site monitoring visits.

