10.5 Informed Consent

Sponsor will provide a sample ICF to the Investigator to prepare for use at his/her site. The site-specific ICF, and any subsequent modifications, must be in agreement with current regulations and guidelines and must be approved by the sponsor prior to submission to the EC. The reviewing EC must approve the ICF before use at the site.

Before participating in the registry, each patient must give written informed consent after the context of the registry has been fully explained in a language that is easily understood by the patient. The patient must also be given the opportunity to ask questions and have those questions answered to his/her satisfaction.

A copy of each patient's signed and dated consent form must be maintained by each investigator in a designated registry administrative file. A signed copy of the consent form must be given to each patient. The consent process must be documented in the patient's medical chart; the documentation should include minimally that consent was obtained prior to participation in the registry, date consent was obtained, and confirmation that a copy of the consent was given to the patient.

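### The documents leave open whether consent may follow the procedure; if some patients do consent late, counting them from the procedure date understates the death component of 30-day MAE

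*Protocol*

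**What the plan says.** Some passages suggest that patients already treated may enter:

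- Registry Synopsis, Registry Design: "Retrospective data collection is allowed for all patients treated in the commercial experience (where applicable".
- Protocol 3.3 says who will be invited: "All patients treated with the commercially available PASCAL Transcatheter Valve Repair System", apart from those in other PASCAL studies.
- Protocol 3.5, inclusion criterion 1: "Patients electively treated or electively intended to be treated with Edwards PASCAL Transcatheter Valve Repair System".

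Others suggest that consent comes first:

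- Protocol 4.3 says that site staff "will approach patients who are candidates for treatment with the PASCAL System to assess their interest".
- Protocol 7 describes treatment of participants in the future tense.

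Three passages are compatible with either order:

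- Protocol 3.3 and 4.3: "A patient will be considered enrolled in the registry once the patient has signed the ICF and the procedure has begun". Both conditions are needed, but no sequence is given.
- Protocol 4.3: "the patient will sign the EC-approved informed consent form (ICF) prior to any data being collected". This ties consent to data collection, not to the procedure.
- Protocol 10.5 requires the chart to show that "consent was obtained prior to participation in the registry, date consent was obtained". This ties consent to registry participation.

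The SAP puts every enrolled patient in the ITT population (4.1) and makes the implanted subset primary (4.2). It sets Day 0 at the index procedure (5.1.1) and defines a censoring day for Kaplan-Meier but no entry day (5.1.3). SAP 8.1 reports composite MAE and each component as counts, percentages and 95% intervals for both populations. The SAP repeats that the design is both prospective and retrospective (2.2), but no analysis uses the distinction and no consent date is defined.

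**The concern.** Written consent is required of every participant, and no waiver for deceased patients is described. A patient who was treated commercially and died before being approached therefore cannot enter. A patient who survived and then consented enters with follow-up counted from Day 0, including days on which death could not have been observed. This is left truncation (immortal time before entry). The SAP handles only right censoring (5.1.3, 6.2).

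All-cause death is a component of the only primary safety measure. The registry is descriptive, so no pass/fail decision depends on the figure, but the reported percentage and its interval are the product. The interval reflects sampling error, not deaths that could never be recorded.

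**Working it through.** The plan gives no figure to reproduce: the minimum of 200 patients has no rate, precision or power behind it. The check is therefore an illustration.

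**Inputs**

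- n = 200 (Protocol 3.3, the planned minimum).
- p, true 30-day death: 2%, 5% or 10%, all assumed. The 10% matches the compassionate-use 30-day mortality in Protocol 1.7.1 and serves as an upper scenario.
- f, the share of enrolled patients who consent after the procedure: not in the documents, so assumed.
- Consent day: not in the documents, so assumed.
- Patients who consent on or before the procedure are taken to have risk p.

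**Consent after day 30.** Late consenters contribute no 30-day deaths, so observed death = (1 − f) × p.

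| f | p = 2% | p = 5% | p = 10% |
|---|---|---|---|
| 0 | 2.0% | 5.0% | 10.0% |
| 10% | 1.8% | 4.5% | 9.0% |
| 25% | 1.5% | 3.75% | 7.5% |
| 50% | 1.0% | 2.5% | 5.0% |

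**Consent at day 15.** Assume a constant hazard over the 30 days and consent unrelated to later risk. With h = −ln(1 − p)/30, observed death = (1 − f)p + f(1 − exp(−15h)). For p = 5%, the late consenters' risk is 2.53%. Then f = 10% gives 0.9 × 5% + 0.1 × 2.53% = 4.75%, and f = 50% gives 0.5 × 5% + 0.5 × 2.53% = 3.77%. The shortfall is about half that for consent after day 30.

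**Planned interval.** Exact binomial 95% intervals at the expected counts, n = 200, consent after day 30:

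| p | f | Expected deaths | 95% interval | Contains p? |
|---|---|---|---|---|
| 2% | 50% | 2/200 | 0.1% to 3.6% | yes |
| 5% | 50% | 5/200 | 0.8% to 5.7% | yes |
| 10% | 25% | 15/200 | 4.3% to 12.1% | yes |
| 10% | 50% | 10/200 | 2.4% to 9.0% | no |

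**Total MAE.** Let q be the non-fatal MAE rate in 30-day survivors who consented on or before the procedure (assumed 5%), and r the rate in patients who consent after day 30. True MAE = p + (1 − p)q. For p = 5% this is 5% + 0.95 × 5% = 9.75%. Observed MAE = (1 − f) × 9.75% + f × r, so the bias is f(r − 9.75%). At f = 50%, r = 5% gives 7.375% (2.375 points too low) and r = 10% gives 9.875% (0.125 points too high). The sign depends on which survivors consent.

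**The case against.** The best defence is that section 4.3 is the operative consent section and describes approaching candidates for treatment. Section 7 also looks forward to treatment. Guide-sheath insertion makes most sense as the event that completes enrolment if the form is already signed. The two limbs of the inclusion criterion could mean implanted versus attempted, mirroring the SAP's two populations. Retrospective collection could mean filling in routine records for patients who had already consented. The sample consent form and the CRF, which might settle the matter, are not in the documents.

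All of this stands as a reason not to assert that late consent will happen. It does not remove the ambiguity: none of these passages forbids consent after the procedure, and the synopsis and sections 3.3 and 3.5 read naturally as admitting treated patients. The death search in section 3.7 ("Edwards may request the site to search death registries as available or applicable per GDPR requirements") does not help, because it covers patients lost to follow-up or withdrawn, who are already in the registry.

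The materiality objection also stands in part. In the scenarios checked, the interval misses the truth only at 10% mortality with half the registry consenting after day 30, and no hypothesis or threshold is at stake.

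A reader might infer that permitting late consent is itself enough to bias the results, that total MAE is understated, or that 1-year mortality is understated by a calculable amount. The documents support none of these. Bias needs patients who actually consent late. The sign for total MAE is open. SAP 9.1 summarises primary cause of death without stating a denominator, so it may not be a mortality percentage at all, and any 1-year effect is secondary.

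**Conclusion.** The point holds conditionally. The documents do not settle the order of consent and procedure. If some patients consent after the procedure, the pooled all-cause death component of 30-day MAE in SAP 8.1 is understated. For consent after day 30 this follows from the entry rule, since those patients have zero 30-day deaths by design. For earlier consent the downward direction also assumes that consenting is unrelated to later risk.

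The size cannot be found from the documents. It is zero if everyone consents beforehand; in the assumed cases with consent after day 30, it is a relative reduction equal to the late-consent share f. This should be fixed, because the primary safety estimate cannot be interpreted until consent timing is known, but it does not invalidate the registry.

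**What to change.** Reconcile the synopsis and Protocol 3.3 and 3.5 with 4.3 and 7, and state whether consent may follow the procedure. If it may not, say so; no analysis change is needed.

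If it may:

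1. Record the consent date in the eCRF, if it is not already captured.
2. Keep Day 0 at the index procedure and the implanted population as primary.
3. In SAP 8.1, report 30-day MAE and its death component separately for patients who consented on or before the index procedure and those who consented after it, in both ITT and implanted populations, with the number of late consenters and their procedure-to-consent intervals.
4. Give no 30-day death interval for patients who consented after day 30. For example, 0/100 would show 0 to 3.6%, but the zero is built in.
5. State survivor selection as a limitation of the pooled figure.

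A Kaplan-Meier estimate of death with delayed entry at consent is optional.

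The cost is a SAP revision and a protocol clarification, which section 10.8 makes a written amendment, across at least 10 sites, plus perhaps one eCRF field; section 10.5 already puts the consent date in the chart. The statistical downside is a wider interval in the group that consented on or before the procedure: for a 10% rate, 6.2% to 15.0% at 20/200 against 4.9% to 17.6% at 10/100 if half consent late.

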1 INTRODUCTION

The PASCAL Transcatheter Valve Repair System is commercially approved in the EU.

1.1 Disease Process

Mitral regurgitation (MR), also known as mitral insufficiency, is the condition in which incompetency of the mitral valve causes abnormal backflow of blood from the left ventricle to the left atrium during the systolic phase of the cardiac cycle. MR is a disease frequently associated with increased morbidity and mortality,¹ and can be characterized by two distinct etiologies: degenerative mitral regurgitation (DMR), and functional mitral regurgitation (FMR). DMR is caused by damage to leaflets or other components of the valve apparatus (e.g. chordae tendinae, papillary muscles). FMR is driven by adverse left ventricular remodeling due to ischemic or non-ischemic myocardial disease.²⁻⁴

1.2 Anatomy and Pathophysiology of Mitral Regurgitation

The mitral valve is an atrioventricular valve, separating the left atrium from the left ventricle (Figure 1). In the normal mitral valve, mitral leaflets coapt during systole to prevent backflow of blood into the left atrium. The mitral apparatus consists of the mitral annulus, mitral leaflets, chordae tendinae, and papillary muscles. The valve itself is saddle-shaped and is a dynamic anatomical structure during the cardiac cycle, playing a crucial role in proper mitral valve coaptation.

[figure not shown]

Figure 1. The Anatomy and Structure of the Mitral Valve and Mitral Apparatus^{5,6}

Initially in MR, patients experience a prolonged asymptomatic period, and if left untreated, may progress to moderate and then severe MR with symptoms such as decreased exercise tolerance and exertional dyspnea.² Eventually, chronic MR imposes volume overload on the left ventricle, which results in cyclical worsening of progressive left ventricular (LV) dilatation, LV remodeling, and cardiomyopathy. This may lead to worsening LV failure, pulmonary hypertension, atrial fibrillation and increased mortality.¹ Although MR may be tolerated for a long time in some patients, in others, the progression of heart failure with LV dysfunction may be more rapid.⁷ The natural course of severe MR depends on many factors including, but is not limited to, the type of MR, the presence of symptoms, LV function and the presence of atrial fibrillation or pulmonary hypertension.⁸ A study of 953 patients with mostly severe FMR (who were considered too high risk for surgery) and were treated with conservative therapy found an annual mortality rate of 26.2%.⁹ Similarly, in high surgical risk patients with severe DMR and NYHA Class III/IV symptoms, annual mortality has been reported to be as high as 34%.¹⁰ The risk of death in subjects aged ≥ 70 years old with moderate or severe MR has been shown to be more than four-fold higher than that of age- and sex-matched subjects with absent or mild MR.¹¹

1.3 Etiology

MR can have many underlying etiologies, but the majority of these can be divided into two major categories: degenerative and functional.¹²

Degenerative mitral valve regurgitation (DMR), also known as primary MR, refers to regurgitation resulting from structural abnormality of the mitral valve leaflets and/or valve apparatus. In the degenerated mitral valve, incomplete coaptation of the mitral leaflets occurs due to prolapse of the leaflets into the left atrium leading to volume overload of the left atrium. DMR is most commonly characterized by mitral valve prolapse (MVP) due to myxomatous degeneration. MVP may be caused by a focal abnormality of a mitral leaflet to involvement of both the anterior and posterior leaflets. MVP may also be due to a flail leaflet (*Figure 2*) which occurs when the leaflet edge, not just the body, is located in the left atrium with free motion.¹³ This situation almost always denotes severe DMR and is strongly associated with adverse outcomes.^{7,14} Thus, the spectrum of DMR may range from lesions from simple chordal rupture involving prolapse of an isolated segment to multi-segment prolapse involving one or both leaflets with significant excess tissue which is characteristic of Barlow's disease (*Figure 3*).^{15,16}

[figure not shown]

Figure 2. Degenerative MR: Prolapse and Flail¹⁷

[figure not shown]

Figure 3. Spectrum of Degenerative Mitral Disease FED: fibroelastic deficiency¹⁶

In contrast, functional mitral regurgitation (FMR), also known as secondary MR, is most commonly a disease of the LV. FMR occurs when the valve and/or valve apparatus are structurally normal, but dysfunction, distortion, or dilation of the left atrial or ventricular chambers results in tethering of leaflets and/or mitral annular dilation that prevents proper leaflet coaptation (*Figure 4*).

[figure not shown]

Figure 4. Mechanism of Functional Mitral Regurgitation: A) normal mitral valve B) ischemic mitral valve with pronounced posterior restriction in P3 after an episode of ventricular ischemia¹⁸

In summary, MR is nearly two separate diseases with different definitions, different therapies, and different outcomes,¹⁹ thus, it is important to distinguish primary/DMR from secondary/FMR as therapeutic approaches and outcomes differ.²⁰

